Exploratory Aim: Examine the differential impact of intervention effects across demographic factors (i.e., marital status, income, adolescent age, and sex).

While evaluating the main effects of interventions is critical to improving health outcomes, it is equally important to examine moderators of randomized clinical trials – even those that are unsuccessful – in order to determine *for whom* interventions may work. Based on findings from the literature and our own earlier work, we will examine potential moderators, with a focus on marital status, income, and adolescent age and sex. Moderators will be tested by including an interaction term with treatment group in the regression models.

Power and sample size:

We plan to enroll 154 subjects so that, after allowing for a 15% attrition rate, 130 subjects will be available for analysis. Preliminary data from our pilot study with 30 adolescents indicates that mean A1C is 9.0% with a standard deviation of 1.16% and a correlation between repeated measurements over time of 0.60. Under these assumptions, we will have 80% power to detect a 0.5% difference in A1C if 122 subjects are measured at all 4 time points or if 138 subjects are measured only twice (out of 4 possible time points). Since we expect to obtain ≥ 3 measurements on most of subjects, enrolling 130 subjects with 2 to 4 measurements each will provide sufficient power for Aim 1. For the SCI (a measure of adherence), using preliminary data in 30 subjects we estimated baseline scores of 23.6 ± 4.2 with a correlation among repeated measures over time of 0.82. With 130 subjects measured at least twice, we will have 80% power to detect a 2.0 unit change due to treatment, which is an 8.5% difference from baseline.

Power calculations for mediation models were considered assuming 130 subjects will be available for analysis. In preliminary data, partial correlations of the mediators, PHQ9 and DFC, with A1C were 0.20 and 0.51, respectively. Correlations of the mediators with treatment were 0.52 and 0.54, respectively. Under these assumptions, we have 63% power to detect an indirect effect of treatment on A1C through PHQ9 and >99% power to detect an indirect effect of treatment on A1C through DFC. Calculations assume a 0.05 significance level.

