Power for moderation will depend on the effect size of the moderation and if the moderator is measured on a continuous or categorical scale. For continuous moderators (adolescent age), we have 80% power to detect a 0.36% change in the treatment effect on A1C per 1-sd change in the moderator. For a binary moderator (frequency 50%), we have 80% power to detect a modification of the treatment effect on A1C of 0.55%. All calculations assume $\alpha=0.05$.

Despite evidence demonstrating the effectiveness of telephone-based CBT to reduce depressive symptoms, there is a chance that mothers who receive the intervention will not report reduced depressive symptoms. If this happens, we would examine the data to determine for whom the intervention works. For example, it may be that a more limited range of scores on the screening tool (PHQ-9) predicts a better response to the intervention.

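### The two moderation power figures do not fit together: 0.36% per SD implies about 0.72%, not 0.55%, for a 50/50 binary moderator

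*Combined protocol and SAP*

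**What the plan says.** All of this is in section 10.0, Statistical Considerations.

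- Test, under the exploratory aim: "Moderators will be tested by including an interaction term with treatment group in the regression models". The moderators of interest are marital status, income, adolescent age and adolescent sex.
- Continuous moderator (adolescent age is the example): "we have 80% power to detect a 0.36% change in the treatment effect on A1C per 1-sd change in the moderator".
- Binary moderator: "For a binary moderator (frequency 50%), we have 80% power to detect a modification of the treatment effect on A1C of 0.55" (per cent).
- Both figures are at alpha 0.05. The moderation paragraph gives no N, residual variance, number of visits or model for either.
- The power paragraph just before it supplies the only inputs available: "mean A1C is 9.0% with a standard deviation of 1.16% and a correlation between repeated measurements over time of 0.60", and "We plan to enroll 154 subjects so that, after allowing for a 15% attrition rate, 130 subjects will be available for analysis".
- For the main effect, "we will have 80% power to detect a 0.5% difference in A1C if 122 subjects are measured at all 4 time points", or if 138 are measured twice.

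**The concern.** The two figures stand in adjacent sentences, at the same power and alpha, for the same kind of test. Their ratio is 0.55/0.36 = 1.53. For a shared model and sample it must be 2, because a 50/50 split has an SD of 0.5.

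Adolescent sex is a named moderator and is binary. As written, the plan tells the reader that the trial has 80% power to find a 0.55% difference in treatment effect between two equal subgroups. If that is optimistic, a null interaction by sex would be read as better evidence of no moderation than it is.

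**Working it through.** **Inputs.** SD 1.16%, correlation 0.60, 130 analysed (122, 138 and 154 also tried) and alpha 0.05, all from section 10.0; 1:1 allocation from section 5.0. The plan does not say one- or two-sided; two-sided is assumed. The multiplier is z = 1.960 + 0.842 = 2.802.

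**Formula.** Let v be the residual variance and SD_M the SD of the moderator. With 1:1 allocation the detectable interaction is z × 2 × √(v/N) / SD_M.
- Moderator in SD units (SD_M = 1): z × 2 × √(v/N).
- 50/50 moderator coded 0/1 (SD_M = 0.5): z × 4 × √(v/N).

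The ratio is 2 whatever v, N, alpha, sidedness or power is used.

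**Check of the inputs on the main effect.** Averaging four visits gives v = 1.16² × 0.70, and averaging two gives v = 1.16² × 0.80. For a 0.5% difference, a t-based calculation gives power 0.806 at N = 122 and 0.802 at N = 138. The plan's main-effect figures therefore reproduce.

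**Reproducing 0.36%.** With the within-subject variance, v = 1.16² × (1 − 0.60) = 0.538, so √v = 0.734. At N = 130: 2.802 × 2 × 0.734/√130 = 0.361%. A baseline-adjusted mean of three follow-ups has v = 1.16² × 0.373. It gives 0.360% at N = 122 and 0.348% at N = 130.

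**The binary figure from the same models.**

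| Residual variance | N | Per SD | 50/50 binary | Power at 0.55% |
|---|---|---|---|---|
| Within-subject (0.40 × SD²) | 130 | 0.361% | 0.721% | 57% |
| Baseline-adjusted mean of 3 (0.373 × SD²) | 122 | 0.360% | 0.719% | 57% |
| Baseline-adjusted mean of 3 (0.373 × SD²) | 130 | 0.348% | 0.697% | 60% |
| Mean of 4 visits (0.70 × SD²) | 130 | 0.477% | 0.954% | 37% |
| Mean of 2 visits (0.80 × SD²) | 130 | 0.510% | 1.020% | 33% |

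The last two rows use the variances that reproduce the main-effect sample sizes. Nine variance models were tried at N = 122, 130 and 138: single measurement, means of visits, change scores, baseline-adjusted means and within-subject. The smallest binary figure was 0.676% (baseline-adjusted mean of three, N = 138). With all 154 enrolled analysed, the same model gives 2.802 × 4 × 0.709/√154 = 0.64%.

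**Possible reconciliations.**
- Rounding: 0.355 to 0.365 per SD gives 0.71% to 0.73%. The stated ratio lies between 0.545/0.365 = 1.49 and 0.555/0.355 = 1.56.
- A different split: this needs SD_M = 0.36/0.55 = 0.655, but a 0/1 variable cannot exceed 0.5.
- A different meaning: each subgroup's deviation from the average effect would be 0.36%, not 0.55%.
- A different variance: 0.55% needs a residual variance (0.72/0.55)² = 1.71 times smaller than the one behind 0.36%.
- A different N: at the same variance it needs 130 × 1.71 ≈ 223 analysed subjects.

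**Power at 0.55%, taking 0.36% as given.** Power is Φ(2.802 × 0.55/0.72 − 1.960) = Φ(0.180) = 0.57, or 0.56 to 0.58 allowing for rounding. With 154 analysed it is 64% on the within-subject variance and 67% with the baseline-adjusted mean of three. Simulation of the interaction test (20,000 runs, N = 130, v = 0.538) gave power 0.779 at 0.36% per SD, 0.565 at 0.55% binary and 0.789 at 0.72% binary.

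**The case against.** **The factor of two is conditional.** The moderation paragraph states no N, variance or model, and the main-effect paragraph itself varies N with the number of visits. Undisclosed, different assumptions for the two figures cannot be excluded. This stands, but then the plan has to state them, and the documents give no hint of any.

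**Either figure could be the wrong one.** If 0.55% were right, the per-SD figure should be 0.275% and 0.36% would be too pessimistic. The text alone does not say which was miscalculated. However, 0.36% can be obtained from the stated inputs. For the binary moderator, even the most efficient model tried, with all 154 enrolled analysed, gives 0.64%. Only forms that divide the within-subject variance by the number of visits fall below 0.55%. They leave out between-subject variation, and they do not give 0.55% either (0.51% for two visits at N = 130).

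**The match to 0.36% came from a search.** The within-subject variance is not the natural one for a between-subject contrast, and the baseline-adjusted mean of three matches only at N = 122. That is fair, and it weakens any claim to know how 0.36% was obtained. It does not affect the ratio.

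**There is another route to 0.55%.** A moderator coded ±1, a single measurement (SD 1.16) and N = 138 give 2.802 × 2 × 1.16/√138 = 0.553%. That is half the subgroup difference, which would itself be 1.11%. It is not the natural reading, and it uses a different variance from the one behind 0.36%.

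**The smaller variance may be legitimate.** The main-effect variances give larger moderation figures, but the planned model accounts for baseline, which could justify a smaller variance. Agreed: that gap is undocumented, not an error in itself.

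**Conclusion.** The two figures are inconsistent as written. With one N, one residual variance and one interaction test, 0.36% per SD goes with about 0.72% for a 50/50 binary moderator. The stated 0.55% is too optimistic under every variance model tried that describes a between-subject comparison with the plan's SD and correlation.

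If 0.36% is kept, power to detect 0.55% is about 57% against the stated 80%. On the two more favourable variances, 80% power would need about 209 to 223 analysed subjects. On the main-effect variances, power is 33% to 37%. These power figures assume a two-sided test, 130 analysed and equal allocation.

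The severity is minor. The aim is exploratory, and neither the planned enrolment of 154 nor the primary analysis depends on the figure.

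**What to change.** State the N, residual variance, number of visits and analysis model used for the moderation calculations, and whether the test is two-sided. Then give the binary figure as twice the per-SD figure from that model:

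- if 0.36% is kept with its variance named, about 0.72%;
- if the main-effect variance is used instead, about 0.5% per SD and about 1.0% binary.

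The first option is enough to remove the contradiction. Add a sentence saying that power for a 0.55% modification is below 80%, so that a null interaction by sex is read accordingly.

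The cost is one figure and one sentence, or two figures under the second option. No participants are added and the analysis does not change; the stated sensitivity for binary moderators becomes less favourable.

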11.0 Privacy/Confidentiality Issues

Confidential participant data will be safeguarded by multiple password protection requirements, data encryption, and locked secure storage of paper documents.

Facebook interactions will be conducted in private (called "secret") Facebook groups. Secret groups allow permissions access to be managed and monitored by the study staff, only allowing approved study participants into the group. Any Facebook users not approved by study staff will not see the group content or that the group exists. All interactions in the group will be extracted using programming stored on a protected server and stored in an SPSS file.

Study participants will be required to "friend" the study Facebook account before they are added to the secret groups to ensure that the correct person is added. All mothers in the study will receive 1 post per day for 3 months. The posts will be on topics related to the group assignment (communication and coping or diabetes education). A moderator will view and respond to all comments made by Facebook group members.

Only Key Study Personnel (KSP) will have access to research information, and all KSP will complete training in Good Clinical Practice.

Participants will be identified with an ID number; names will not be included on any data outside of RedCAP. Only research staff who have completed IRB training and have been added as KSP have access to the study RedCAP. All identifying information will be destroyed at the earliest possible time following completion of the study. All data will be analyzed by groups, with no potential for individual patients to be identified. Any publications arising from the study will not contain personal information. Digital files will be erased after completion of the study.

12.0 Follow-up and Record Retention

Duration of the study is anticipated to be 5 years. All data will be analyzed by groups, with no potential for individual patients to be identified. Any publications arising from the study will not contain personal information.

Research records will be maintained for at least three (3) years from the date the research is closed with the IRB. All Health Insurance Portability and Accountability Act (HIPAA) related documentation will be maintained for at least six (6) years from the date of the last use or disclosure of the Protected Health Information (PHI).
